2.6 Design and Procedures

2.6.1 Study Design

The protocol is a prospective, randomized, double-blinded, crossover study in 75 subjects (target, 60 evaluable) with Major Depressive Disorder (MDD) receiving bupropion HCl 300mg XL (branded or generic). Subjects will be studied for a total of approximately 28 weeks: an approximately 4 week lead-in phase during which participants remain on their existing bupropion product, and then four randomized cross-over phases of approximately 6 weeks on each of the four bupropion study drugs (brand and 3 generics). For each of the four bupropion products, subjects will have (a) formal pharmacokinetic evaluation (24 hr plasma and urine) at steady-state, (b) every 3-week in-person standard structured clinical evaluations of depressive symptoms and side effects, and (c) once daily smart phone-based assessments to capture information on symptoms and side effects. See Figure 1 for a pictorial description.

[figure not shown]

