2.6.5 Randomized Study Period

Subjects will take each 300mg bupropion XL product for 6 weeks, and then be switched to another product without washout, according to their randomization schedule. During the 2nd-3rd week on each product, subjects will visit the study clinic for a bupropion pharmacokinetic session, an objective assessment of depression and side effects, and to receive another 3 week supply of study drug. During the 6th week on each product, subjects will again visit the study clinic for objective assessments of depression and side effects. Subjects will then be switched to their next scheduled drug product, and the sequence repeated for the four study drugs. Each subject will therefore be studied for four 6-week study drug epochs. Subjects will not be informed when they are being switched, in order to minimize bias. A Medication Event Monitoring System, (MEMS 6 TrackCap, or equivalent) will be used to assess compliance and compile drug dosing histories for the quantitative analysis of adherence during each subject's 28 week study period.

The rationale for the timing of the pharmacokinetic assessments is as follows: Subjects must be at steady-state on their new bupropion product. Steady-state bupropion concentrations have been reported to occur by 8d for all formulations. ¹⁸ Nevertheless, to ensure that metabolites disposition is also at steady-state, and metabolite elimination is known to be somewhat slower than parent, at least 10d will be allowed before assessing pharmacokinetics. Assessment should not wait too long, however, in case a patient reports loss of effectiveness or side effects after starting a new bupropion product, causing a product switch or other intervention, and this risk increases with time. Therefore the 10-20 day window will be targeted for the bupropion pharmacokinetic session for each product.

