2.6.5.1 Bupropion Pharmacokinetic Sessions

Subjects will be studied in the Clinical Research Unit at Washington University-Barnes Jewish Hospital, and remain in the Unit for approximately 24 hours. Subjects are instructed to 1) have nothing to eat or drink after midnight before the study session and 2) abstain from alcohol for 24 hours before each study period and until the last sample is collected. Because food increases plasma C_{max} and AUC of bupropion extended-release tablets by 11 and 17%, respectively (although changes were not statistically significant¹⁸), subjects will nonetheless be studied after an overnight fast to minimize potential variability. They will take their study drug with 240ml of water, receive a standard meal 4 hours after bupropion dosing, and have free access to food and water thereafter. An intravenous catheter will be placed by CRU CONFIDENTIAL: This document is the intellectual property of [name], PhD. Acceptance of this document constitutes the agreement by the recipient that no unpublished information contained herein will be published or disclosed without prior written approval.

nursing staff in an arm vein for blood sampling (5cc, EDTA) immediately before and 1, 1.5, 2, 3, 4, 5, 6, 7, 8, 10, 12, 16, 20 and 24 hr after dosing (15 samples, 75 cc per session, 300 cc over the entire study), and samples centrifuged to obtain plasma. Urine will be collected for 24 hr, kept refrigerated, the volume measured, and aliquots frozen. Samples will be stored at -80°C in the PIs lab. At the end of the 24 study, the intravenous catheter is removed, and subjects leave the research unit. Plasma and urine concentrations of bupropion, hydroxybupropion, erythrohydrobupropion, and threohydrobupropion will be determined using a chiral LC/MS/MS assay.

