2.7.3 Statistical Methods

2.7.3.1 Bioequivalence

Bioequivalence will be determined essentially per FDA Guidance, 9,10 using an average bioequivalence approach. A repeated measures model will be fit for each parameter separately. Interpatient variability for each compound will be examined separately prior to assuming that they are all the same. It is anticipated that most parameters will be log-transformed prior to statistical testing, but the distributional assumptions will be examined for each parameter and the most appropriate data transformation used. Following the standard FDA guidance the two one-sided test procedure will be used to determine whether each generic product is significantly less bioavailable than Wellbutrin XL, and whether Wellbutrin XL is significantly less bioavailable than each generic product. This is expressed as a limit of test average/reference average of 80% for the first statistical test and a limit of reference average/test average of 80% for the second statistical test. In practice, the 90% confidence interval around the geometric means of the test/reference ratio for each parameter must be entirely between 0.80 and 1.25 for bioequivalence.

Bioequivalence will be determined using the standard pharmacokinetic parameters (AUC and C_{max}) and equivalence definition (90% CI of the generic/brand geometric mean is within 80-125%) for bupropion (primary), the active metabolite hydroxybupropion (secondary), and for the other metabolites (tertiary). The test for each generic compound will not be adjusted for the other comparisons, e.g. to control the study-wide error rate. Similarly, analysis will not control for multiple comparisons involved in testing each of the parameters. As an aid to interpretation of the results, however, the False Discovery Rate will be computed for the observed results. The generics will also be evaluated using the criteria for bioequivalence for narrow therapeutic index drugs (90% CI of ratio within 0.95-1.05).

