The influence of *CYP2B6* genetics on the disposition of bupropion, hydroxybupropion, and bioequivalence between brand and generic bupropion XL products will be determined through exploratory analyses to fit individual bioequivalency models by adding random effects for each agent and covariances between the responses. Order effects (omitted in the model described above) will also be determined. Predictors of overall response of each individual for each parameter, CONFIDENTIAL: This document is the intellectual property of [name], PhD. Acceptance of this document constitutes the agreement by the recipient that no unpublished information contained herein will be published or disclosed without prior written approval.

especially CYP2B6 genetics, will be evaluated, specifically the most common variant allele *CYP2B6*6*, comparing *CYP2B6*1/*6* and *CYP2B6*6/*6* genotypes with non-carriers of *CYP2B6*6*, and with true *CYP2B6*1/*1* genotypes.

The influence of stereochemistry on (i) bupropion disposition, (ii) bupropion bioactivation to hydroxybupropion, and (iii) bioequivalence between bupropion XL products will be examined by fitting an expanded model where both the enantiomers and diastereomers will be included by introducing an additional factor, examining the significance of this factor, and its interaction with the specific compound.

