4. HUMAN SUBJECTS RESEARCH

4.1 Protection of Human Subjects

4.1.1 Human Subjects Involvement and Characteristics

The 28-week prospective, randomized, double-blinded, crossover study will involve enrollment of 75 subjects age 18-75 vrs who volunteer and meet all inclusion/exclusion criteria. All subjects will have been diagnosed with Major Depressive Disorder (MDD) and be taking bupropion HCl, 300mg XL (branded or generic versions). After all study related procedures, risks and benefits are explained and discussed, potential subjects will be asked to sign an informed consent form approved by the Washington University Institutional Review Board (IRB) and will be enrolled. The randomization table will be generated and kept by the Barnes-Jewish Hospital Investigational Pharmacy. Subjects will complete baseline research assessments conducted by trained research staff which include a) diagnostic and symptomatic measures of depression, b) review of medical conditions and medications, c) alcohol and drug use, and d) physical health. Subjects will remain on their own medication for the initial 4 weeks of the study. During this time they will undergo daily monitoring with smart phone-based Ecological Momentary Assessments (EMA). Upon completion of this 4 week period, subjects will visit the clinic for assessment of depression and side effects. Non-adherent subjects will be withdrawn from the study. Ongoing study participation will include 6 weeks on each of the four bupropion products (brand and 3 generics) without washout between drug crossover. Subjects will participate in overnight pharmacokinetic sessions at the Washington University Clinical Research Unit (CRU) approximately 2-3 weeks following each drug crossover. These sessions will occur 4 times and involve collection of blood and urine samples for up to 24 hours. Subjects will be provided with 3 weeks of study drug prior to discharge from the CRU. Periodic (approximately every 3 weeks) interviews will be conducted at WU Medical Center research offices and include monitoring of drug compliance (MEMS 6 TrackCap system), structured interview for assessment of depression symptoms, completion of Montgomery-Asberg Depression Rating Scale (MADRS) and assessment of drug effect(s). Subjects will receive an additional 3 week supply of study drug at each clinic visit. Subjects will complete smart phone-based EMA daily for real-time capture of patientreported drug effects. Phones will also be used as a reminder to adhere to dosing instructions and provide instructions and trouble-shooting guidance. At the conclusion of the final session and last clinic visit, subjects will be returned to their original bupropion formulation and directed to resume their own medication. All studies are conducted under the supervision of the PI, a Board-Certified and GCP-certified and clinically active anesthesiologist with extensive experience in the conduct of human volunteer studies. We will examine bioequivalence, clinical equivalence, stereoselectivity, genomics, and patient perspectives regarding switches between commercially available forms of bupropion 300mg XL.

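### With one pharmacokinetic profile per product, the exploratory individual-bioequivalence model for CYP2B6 cannot separate subject-by-product variance from within-subject variance

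*Combined protocol and SAP*

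**What the plan says.** The main analysis in section 2.7.3.1 is done "using an average bioequivalence approach", and "A repeated measures model will be fit for each parameter separately". The same section then turns to CYP2B6. Its influence on bupropion and hydroxybupropion disposition, and on brand-generic bioequivalence, is left to exploratory analyses that are "to fit individual bioequivalency models by adding random effects for each agent and covariances between the responses". The text does not say whether a residual term stays in that model or which covariance structure is used, and it writes no genotype-by-product term. It does separately plan to evaluate predictors of each subject's overall response, comparing \*1/\*6 and \*6/\*6 with non-carriers of \*6 and with true \*1/\*1.

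The design gives one profile per product:

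- Section 2.6.1 has four crossover phases, one for each of the four products.
- Section 2.6.5: "Therefore the 10-20 day window will be targeted for the bupropion pharmacokinetic session for each product".
- Section 4.1.1: "These sessions will occur 4 times and involve collection of blood and urine samples for up to 24 hours".
- Section 2.6.5.1 gives the blood volume as "15 samples, 75 cc per session, 300 cc over the entire study".
- Section 2.6.4 describes only depression and side-effect assessments at the lead-in clinic visit, and the Study Table lists pharmacokinetic sampling only in the four study-drug periods.

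**The concern.** Average bioequivalence compares product means. Individual bioequivalence also asks whether the difference between two products varies from one subject to the next, beyond ordinary variation when the same subject takes the same product again. Separating those two sources requires at least one product to be given and sampled more than once in the same subject. Here none is. The 15 samples in a session yield one AUC and one Cmax; they are not repeat administrations.

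The section therefore assigns a stated scientific question, whether CYP2B6 alters brand-generic bioequivalence, to a model whose name promises something the data cannot supply. An analyst who keeps a residual gets a split between the two variances that the data do not determine. If that split were interpreted, ordinary within-subject variation could be described as individual differences between products.

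**Working it through.** **Inputs.** Four products, one value per product per subject (sections 2.6.1, 2.6.5 and 4.1.1); each parameter modelled on its own (2.7.3.1); 60 evaluable subjects (2.5). Cross-check of the session count from section 2.6.5.1: 15 samples x 5 cc = 75 cc per session, and 75 x 4 = 300 cc, as stated. The plan gives no variance, power or sample size for this analysis, so there is no figure of its own to reproduce.

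**Step 1: count the variance parameters.** The four values per subject have a 4x4 covariance matrix V with 4 variances + 6 covariances = 10 distinct elements. Let the random product effects have variances g_ii and covariances g_ij, and let s² be the residual variance. Then

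- V_ii = g_ii + s²
- V_ij = g_ij for i ≠ j.

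Adding any amount c to s² and subtracting c from every g_ii leaves V unchanged. Ranks of the map from parameters to V:

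| Model | Parameters | Rank |
|---|---|---|
| Random effect per product, free covariances, common residual | 11 | 10 |
| Same, product-specific residuals | 14 | 10 |
| Subject intercept, common subject-by-product variance, residual | 3 | 2 |
| Subject intercept, product-specific effects, residual | 6 | 5 |
| Unstructured 4x4 covariance, no separate residual | 10 | 10 |

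Each version that keeps a residual beside product-level random effects is short by at least one. For comparison, if every product were given twice, a random effect per product plus product-specific residuals would have 14 parameters and rank 14.

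**Step 2: show that the data do not inform the split.** Illustration with simulated data, 60 subjects, assumed between-subject variance 0.40² = 0.16, and subject-by-product (D) plus within-subject (W) variance summing to 0.09. The difference between two products has variance 2D + 2W.

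| D | W | 2D + 2W | Log-likelihood |
|---|---|---|---|
| 0 | 0.09 | 0 + 0.18 = 0.18 | -96.595 |
| 0.02 | 0.07 | 0.04 + 0.14 = 0.18 | -96.595 |
| 0.05 | 0.04 | 0.10 + 0.08 = 0.18 | -96.595 |
| 0.08 | 0.01 | 0.16 + 0.02 = 0.18 | -96.595 |

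The fit is identical in every row. So is the variance of a product difference, which is all that the average-bioequivalence and genotype-by-product comparisons need.

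**Step 3: check the replacement.** Fixed effects: intercept 1 + product 3 + period 3 + genotype 2 + genotype-by-product 6 = 15 columns. With 60 x 4 = 240 rows the design has rank 15, so the interaction is estimable. A two-group version of the test (36 carriers of \*6 against 24 non-carriers, Hotelling's T² on product contrasts, unequal variances across products, no period effects, 4000 simulated trials) had size 0.046 at nominal 0.05.

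**Step 4: precision, under assumptions.** Section 2.2 reports genotype counts of 17, 20 and 6 (43 in all) in a previous study. Scaled to 60 they give 23.7, 27.9 and 8.4, taken as 24, 28 and 8. The plan gives no within-subject CV; 15% to 40% is assumed, and the CV stands for the inseparable sum of the two variances. With s_w = √ln(1 + CV²), SE = √2 · s_w · √(1/a + 1/b) and a + b − 2 degrees of freedom, the ratio of generic/brand ratios detectable with 80% power at two-sided 0.05 is exp[(t_0.975 + t_0.80) · SE].

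| Contrast | CV 15% | CV 40% |
|---|---|---|
| \*6 carriers (36) v non-carriers (24) | SE 0.056, ratio 1.17 | SE 0.144, ratio 1.51 |
| \*6/\*6 (8) v non-carriers (24) | SE 0.086, ratio 1.28 | SE 0.222, ratio 1.90 |

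**The case against.** The best defence is that the sentence names no residual. A variance for each agent plus covariances can be read as an unstructured 4x4 matrix, which this design supports. Section 2.7.3.1 lends that reading some weight, because it plans to examine variability for each compound separately before assuming equality. This stands: a reader might infer that the model cannot be fitted at all, and the documents do not support that. It does not rescue the stated purpose, however. In the unstructured matrix each product's variance still mixes the two components, so the fitted model does not measure individual bioequivalence.

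A reader might also infer that the CYP2B6 question cannot be answered, or that within-subject noise could pass for a genotype effect. Neither follows. Genotype varies between subjects, and its interaction with product is judged against the variance of within-subject product differences, which is the same under every split in step 2. CYP2B6 is also examined elsewhere: as a predictor of overall response in the same section, and as a covariate alongside product in the optional population pharmacokinetic analysis of section 2.7.2.

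Finally, the analysis is labelled exploratory, and the plan sets no individual-bioequivalence criterion, limit or decision rule. Section 4.4 does foresee examining the pharmacokinetics of a participant who relapses or has side effects, to determine bioequivalence, but it does not tie that to this model. There is thus no planned declaration to overturn. What remains is an analysis named for something the design cannot deliver.

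**Conclusion.** The point holds, at low severity. With one profile per product, subject-by-product variance and within-subject variance are inseparable: 11 parameters for 10 elements if a residual is kept, and an identifiable covariance that is not individual bioequivalence if it is not. This rests on two readings of the plan: no product is sampled twice in any subject, which the session count and blood volume confirm, and each parameter is modelled on its own, as section 2.7.3.1 says.

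It would be a mistake to carry this over to the primary analysis. Average bioequivalence uses only the variance of product differences, which is identified, so those conclusions are unaffected. The detectable ratios in step 4 depend on an assumed CV and genotype mix and are there only to show that the \*6/\*6 comparison would be imprecise if the group is about that small.

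**What to change.** In section 2.7.3.1:

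1. Drop the individual-bioequivalence label, or state that subject-by-product and within-subject variance cannot be separated in this design and will not be interpreted.
2. Specify the covariance as an unstructured 4x4 within-subject matrix with no additional residual term.
3. Write the CYP2B6 test explicitly as a fixed genotype-by-product interaction in the average-bioequivalence model.
4. Report genotype-specific generic/brand ratios with 90% CIs, and note that precision for \*6/\*6 is likely to be low if few such subjects enrol.

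The cost is analysis wording only, with no new visits, samples or subjects. An exploratory claim about individual subjects is given up. Recovering it would need repeat administration and sampling of products, which is a different design.

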2.7.3.2 Patient perception of antidepressant effectiveness and side effects

Patients' self-reported clinical differences (release patterns, antidepressant effectiveness, and adverse events) will be compared between all bupropion 300mg XL products (brand vs. generics, and between generics).

Reports will be determined by the daily patient smart phone assessments. Daily depressive symptom scores, side effect scores, and focus group-nominated symptoms (e.g., sensations regarding drug release) during each randomized bupropion phase will be compared with each other, and with those from the open-label lead-in period. Repeated measures ANOVA analogues of the models described above for the pharmacokinetic parameters will be used for assessing patents' perceptions. Since there are no well-accepted criteria for the equivalence of scores using this method, any systematic effects of differences between patient's responses to Wellbutrin XL and each generic product will be tested.

Analysis will explore whether differences in smart phone-collected depression symptoms, side effects, and patient reports regarding release patterns are related to pharmacokinetics by augmenting the models above with pharmacokinetic parameters as covariates. Analysis will determine if there are differences in bupropion products by correlating, on an individual basis, the ratio of the two pharmacokinetic parameters to the difference in symptoms or side effects.

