2.7.3.3 Objective evaluation of antidepressant effectiveness

The main clinical outcome is relapse of depression, defined using the MADRS and SCID depression module. Patients with a 2 point or greater increase from their average baseline open-label lead-in phase MADRS score, and/or MADRS score of 15 or greater, will have the SCID depression module conducted. If the SCID reveals current MDD, they will be considered to have relapsed. Physician adjudication (by study Psychiatrist, who is blinded to randomization assignment) will be utilized as well.² An appropriate generalized linear model with a binomial link function will be used. Relapse of depression will also be considered an end-point in the study.

Subjects suffering a relapse will be removed from the study and will return to their pre-study bupropion product. Subjects will be advised to contact their treating physician for follow-up. Data and specimens collected for these subjects will be included in the analysis.

The secondary clinical outcomes are symptomatic change in depression (MADRS scores) and side effects (Antidepressant Side Effect Checklist scores) determined at the every 3-week interviews. Repeated measures ANOVA analogues of the models described above will be used for each of these analyses. Analysis will test for any systematic effects of differences between patient's symptom/side effect levels with Wellbutrin XL and each generic preparation.

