2.7.4 Sample Size Justification

Calculations for sample size and power of the proposed studies are based on information from the confidence intervals for the ratio of the pharmacokinetic parameters for the generic (Budeprion XL) to the innovator (Wellbutrin XL) which was recently reported by the FDA in their evaluation of Budeprion XL.⁵¹

SAS 9.3's Proc Power was used to conduct the correct power analysis for the two one-sided tests (TOST) approach per the FDA guidance on bioequivalence. Using a 90% confidence interval and ratios needing to be between 0.80 and 1.25, the power for sample sizes ranging from a conservative estimate of 60 to the recruitment goal of 75 was computed. If the comparators are indeed bioequivalent (ratio=1.0) then the study power would be >0.999 for a pharmacokinetic parameter such as AUC and 0.98 for a more variable parameter such as C_{max} . If the generic is 10% under (or over), e.g. ratio=0.90,

then for AUC the power would be 0.78=0.83 to declare a significant difference between the compounds at an alpha of .05 even if the CI for the ration was still contained within the 0.80-1.25 bounds.

Ver 1.02

The study is also powered in order to have a reasonable power of detecting clinical differences between compounds. If one of the generics is non-equivalent with respect to symptom and it is assumed that 25% suffer a relapse on this generic versus 5% for Wellbutrin or other (equivalent) forms, then using a McNemar's test for equality of proportions, a sample size of 60 and a 1-tailed alpha of 0.05, the power will be about 0.83. For continuous variables, there will be 0.80 power to detect a standardized difference of 0.37 (low-medium effect size).

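### The primary bioequivalence model leaves out order (period) effects and the clinical score models inherit it, costing power and, if removal differs by product, biasing the product contrast

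*Combined protocol and SAP*

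**What the plan says.** Section 2.7.3.1 sets out the decision model without listing its factors: "A repeated measures model will be fit for each parameter separately". The 90% confidence intervals for the test/reference ratios come from this model. Later in the same section, in a paragraph that opens with exploratory genetic analyses, the plan adds: "Order effects (omitted in the model described above) will also be determined". It gives no rule for carrying an order effect, once found, back into the primary intervals.

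The clinical scores take over the same structure. For the phone assessments (2.7.3.2): "Repeated measures ANOVA analogues of the models described above for the pharmacokinetic parameters will be used". For MADRS and the side-effect checklist (2.7.3.3): "Repeated measures ANOVA analogues of the models described above will be used for each of these analyses". Neither section adds a period term. These are tests for a difference, not for equivalence: "any systematic effects of differences between patient's responses to Wellbutrin XL and each generic product will be tested".

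Three further statements matter. Order is randomized and balanced (2.6.2). Subjects who relapse leave the study, but "Data and specimens collected for these subjects will be included in the analysis" (2.7.3.3). And the sample size section (2.7.4) considers a non-equivalent generic on which "25% suffer a relapse on this generic versus 5% for Wellbutrin or other (equivalent) forms".

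**The concern.** In a four-period crossover lasting 24 randomized weeks, scores may move with time whatever the product. The plan itself reports, in 2.6.5, that symptoms rose at randomization in an earlier study. Without a period term, two things follow.

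- **Complete, balanced data.** A shift cancels from the product contrasts but stays in the residual. Standard errors are too large and the difference tests lose power. For bioequivalence this errs on the conservative side and cannot create false equivalence.
- **Removal that depends on product.** Periods are no longer balanced over products, so the shift no longer cancels and the contrast is biased.

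At stake are objectives 2 and 3, which rest on the clinical difference tests, more than the 80–125% conclusion. The relapse GLM is a separate model and is not part of this point. A period term would not deal with carryover.

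**Working it through.** **Inputs.** n = 60 evaluable; four periods, order balanced (2.6.2; a balanced 4×4 arrangement is assumed); 0.80 power at 0.37 (2.7.4); removal 25% versus 5% (2.7.4). The size and shape of the shift are assumptions, in units of the within-subject SD, σ. The SD of a paired difference is √2·σ.

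**The plan's own figure.** The claim is "there will be 0.80 power to detect a standardized difference of 0.37". A paired t-test with n = 60, two-sided α = 0.05 (assumed, not stated for this line) and noncentrality 0.37·√60 = 2.866 gives 0.805, so the figure is reproduced. A one-sided test gives 0.883 and two parallel groups of 60 give 0.527.

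**Complete data.** There are 240 observations. Residual df without period = 240 − 60 − 3 = 177; with period, 174. Leaving period out multiplies the expected residual variance by

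1 + n·Σ(p_k − p̄)² / (177·σ²).

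For total shift D (in σ), Σ(p_k − p̄)² is (5/9)·D² for a linear drift and 0.75·D² for a rise in the first period only. The multiplier is therefore 1 + 0.188·D² or 1 + 0.254·D², and its square root is the SE ratio. Power without the term is the chance that the noncentral t exceeds the critical value times that ratio.

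| Shift | SE ratio | Power without period, formula (simulation) | Power with period, formula (simulation) |
|---|---|---|---|
| Linear 0.5σ | 1.023 | 0.801 (0.800) | 0.813 (0.814) |
| Linear 1σ | 1.090 | 0.762 (0.769) | 0.813 (0.818) |
| First period 0.5σ | 1.031 | 0.796 (0.797) | 0.813 (0.814) |
| First period 1σ | 1.120 | 0.744 (0.743) | 0.813 (0.812) |

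Simulations used 20,000 runs. For the 1σ linear drift the simulated type I error is 0.032 without period and 0.048 with it, so the test without period is conservative. If the shift is measured in SDs of the paired difference, 1 SD equals 1.41σ, and power without period is 0.708 (linear) or 0.671 (first period).

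**Bioequivalence.** The within-subject log SD is back-solved from 2.7.4.

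- Cmax: 0.98 power at ratio 1.0 gives 0.304.
- AUC: reading the 0.78 at ratio 0.90 as a difference test gives 0.208. Reading it as TOST gives 0.264, but that implies only 0.997 at ratio 1.0, against the plan's figure of above 0.999. An SD of 0.246 gives 0.999.

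A 20% linear drift is log 1.2 = 0.182, so D = 0.182/SD. TOST power:

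| Log SD | SE ratio | Ratio 1.0, without / with | Ratio 0.90, without / with |
|---|---|---|---|
| 0.208 | 1.070 | – | 0.907 / 0.924 |
| 0.246 | 1.051 | 0.999 / 0.999 | 0.809 / 0.832 |
| 0.304 | 1.033 | 0.979 / 0.982 | 0.662 / 0.683 |

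**Product-dependent removal.** Removal is 25% on one generic and 5% on each other product, with data up to removal kept and later periods lost. Simulated bias in generic minus brand for a 1σ shift (2,500 runs, Monte Carlo error 0.004):

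| Design and shift | Without period | With period |
|---|---|---|
| Williams, n = 60, linear | +0.065 | −0.010 |
| Williams, n = 60, first period | −0.074 | +0.002 |
| All 24 orders, n = 72, linear | +0.078 | +0.001 |
| All 24 orders, n = 72, first period | −0.085 | 0.000 |
| Equal 10% removal, linear | −0.002 | −0.001 |

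A separate expected-value calculation over all 24 orders gave −0.06 to −0.08 (first period) and +0.06 to +0.07 (linear) per unit shift without period, and zero with it. For PK at a 20% drift, exp(0.065 × 0.182) − 1 = 1.2% to exp(0.085 × 0.182) − 1 = 1.6% of the ratio.

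Power at 0.37 under this removal, with a shift of 0.5 SD of the paired difference: first-period rise, 0.58 without and 0.72 with period; linear rise, 0.78 without and 0.72 with. In the linear case the bias points away from zero, so the higher figure is not a gain.

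**The case against.** **The word order may mean sequence.** Elsewhere (2.6.2, 2.6.3, 4.1.4) it refers to the assigned sequence of products, and 2.7.3.1 lists no factors. The ambiguity is real. But on either reading nothing puts period into the model, so the conclusion is the same.

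**No shift size is documented and the design guards against one.** Over-encapsulation starts in the lead-in, subjects are not told when they switch, and the lead-in familiarizes them with the assessments (2.6.4, 2.6.5). For PK, dosing is stable, sessions are fasted and adherence is monitored. This stands as a reason to expect small shifts. At 0.5σ, power without period is still about 0.80; a clear loss needs about 1σ. If the 0.37 was standardized by an SD that already contains period variance, the stated 0.80 is not eroded, and the period term would instead add power.

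**The bias is small and needs two conditions.** A 0.5σ shift gives about 0.03–0.04σ, against a target of 0.37 × √2 = 0.52σ, and the sign depends on the shape of the shift. The 25%/5% scenario implies 1 − 0.75 × 0.95³ = 36% removal, above the 25% drop-out assumed in 2.5. The re-derivation also lets removal depend on product only, not on the subject's own MADRS score. All of this limits the size, not the direction of the advice.

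**Order effects will be examined anyway.** They will, but outside the decision model and with no rule for using the result, which leaves the choice of model until after the data are seen.

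**Conclusion.** The concern holds, as a conditional one. The primary model has no period term and the phone, MADRS and side-effect models follow it. If scores shift between periods, the clinical difference tests lose power: about 1–2 points for 0.5 within-subject SD and 5–7 points for 1 SD with complete data. Under the plan's own unequal-relapse scenario the product contrast is biased by 0.06–0.09 times the shift, which a period term reduces to 0.01 or less. The effect on the 80–125% decision is negligible with complete data and 1–2% of the ratio under unequal removal, both at an assumed 20% drift. These figures rest on assumed shift sizes, a balanced design, a two-sided 5% test and the back-solved PK SDs. The change should be made because it costs almost nothing, not because a large error is certain.

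**What to change.** In 2.7.3.1, prespecify the primary model for log AUC0-24 and log Cmax as product and period (1 to 4) as fixed effects with a random subject effect, using all available periods, and take the 90% confidence intervals from that model. Remove the parenthesis saying that order effects are omitted, and say whether period, sequence or carryover is meant where order is mentioned. A sequence term is optional; it would use between-subject degrees of freedom. In 2.7.3.2 and 2.7.3.3, state that the phone, MADRS and side-effect models include the same period term.

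The cost is wording plus 3 of 177 residual degrees of freedom. With no shift and complete balanced data, the SE of a product difference is σ·√(2/60) = 0.183σ with or without the term.
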